- 682 • HbA1c level will be measured using the DCA Vantage or similar point-of-care device or local
683 lab
- 684 • Group B participants will complete the PLGS usability survey (see Chapter 7)
- 685 • All applicable study supplies will be returned to the clinic

688 CHAPTER 6: STUDY DEVICES

689

690 6.1. Description of the Investigational Device

[figure not shown]
691 6.1.1. Insulin Pump

692 The Tandem Diabetes ambulatory infusion pump with PLGS (t:slim X2 with Basal-IQ Technology) is
693 intended for the subcutaneous delivery of insulin for the management of diabetes mellitus in persons
694 requiring insulin. A touch sensitive Liquid Crystal Display (LCD) provides both the pump information
695 to the user as well as the interface for the user to program insulin delivery timing and quantity, both
696 basal and bolus delivery of insulin at set and variable rates.

697 Additionally these pumps are integrated with and display continuous glucose data (CGM) and contain
698 a Predictive Low Glucose Suspend (PLGS) algorithm which allows the user to set the system to
699 automatically suspend delivery of insulin when the predicted glucose value falls below a predefined
700 threshold.

702 The device system components include an insulin pump and cartridge, infusion catheter, CGM sensor
703 and transmitter, and a blood glucose meter for CGM calibrations.

705 706 Figure 3 - Tandem Pump Showing Labeled Components

707 708 709 6.1.2. Continuous Glucose Monitoring

710 The study CGM will include an unmodified Dexcom G5 Mobile transmitter and sensors. This is an
711 FDA-approved device system with no changes to its hardware or firmware components. The CGM
712 sensor will be replaced at least once every seven days.

713 714 6.1.3. Blood Glucose Meter and Strips

715 Blood glucose levels will be measured and the CGM device will be calibrated using the Accu-Chek
716 Guide Blood Glucose Monitoring System in accordance with the manufacturer labeling.

717 718 6.1.4. Ketone Meter and Strips

719 Blood ketone levels will be measured using the Abbott Precision Xtra meter and strips in accordance
720 with the manufacturer's labeling. The blood glucose meter component of the Precision Xtra device will
721 not be used.

722

723 **6.2. Study Device Accountability Procedures**

724 Device accountability procedures will be detailed in the study procedures manual.

725

726 **6.2.1. Blood Glucose Meter Testing**

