1163 structure will be fit for percent time below <70 mg/dL to compare the two treatments. The
1164 model will adjust for period as a covariate. If residual values from the regression model have a skewed
1165 distribution then an appropriate transformation or a nonparametric analysis based on ranks will be
1166 performed.
1167

1168 There will be no imputation of missing CGM data.
1169

1170 **10.7. Analysis of the Secondary Endpoints**
1171 Analysis of the secondary endpoints and additional CGM metrics will parallel the analysis of the
1172 primary endpoint above.
1173

1174 **10.8. Safety Analyses**
1175 The following safety outcomes will be tabulated by participant within each 3-week treatment period.
1176 The summary statistics will include start date, stop date, severity, relationship, resolution, and duration.

- Diabetic ketoacidosis (DKA), as defined by the Diabetes Control and Complications Trial (DCCT).
- Severe clinical hypoglycemic events such that the participant required assistance from another person to actively administer carbohydrate, glucagon, or engage in other resuscitative actions; note severe hypoglycemia could be considered both and efficacy and safety outcome
- Ketosis events (blood ketone level >1.0 mmol/L)
- All other reported adverse events
- Unanticipated adverse device effects

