207 Each of the secondary outcomes will be calculated separately for sensor values during daytime (6:00
208 AM to just before 10:00 PM) and sensor values during nighttime (10:00 PM to just before 6:00 AM).

209 The primary outcome, percentage of glucose sensor values < 70 mg/dL, will also be divided into
210 daytime and nighttime periods as an additional secondary outcome.
211
212 For all secondary outcomes separated by time of day, summary statistics appropriate to the distribution
213 will be tabulated by treatment group. The same model described above for the primary and secondary
214 analyses will be fit with the inclusion of a treatment by time of day interaction. The p-value for the
215 interaction term will be reported. These analyses will be conducted to determine whether a similar trend
216 to the overall treatment effect is seen in the different times of day. An appropriate transformation or a
217 nonparametric analysis based on ranks will be applied to all highly skewed secondary outcomes.
218
219 The study is not expected to have sufficient statistical power for definitive conclusions in the secondary
220 analyses by time of day, and statistical power will be low to formally assess a treatment by time-of-day
221 interaction. Interpretation of the analyses by time of day will depend on whether the overall analysis
222 demonstrates a significant treatment effect. In the absence of any significant treatment effects in the
223 overall analyses, assessment of secondary analyses by time of day will be considered exploratory and
224 used to suggest hypotheses for further investigation in future studies.
225

226 **8. Safety Analyses**

227

228 Safety outcomes will be tabulated by participant for all adverse events from enrollment to the final study
229 visit or final adverse event, whichever comes later.
230

231 **8.1 Definitions**

232 Reportable adverse events for this protocol include severe hypoglycemia (SH), diabetic ketoacidosis
233 (DKA), and any other untoward medical occurrence that meets criteria for an adverse event (AE) or
234 serious adverse event (SAE). Device deficiencies that could have led to an adverse device effect will
235 also be reported.
236

237 Hypoglycemic events will be considered severe if the participant required assistance from another
238 person to actively administer carbohydrate, glucagon, or engage in other resuscitative actions. This

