239 means that the subject is impaired cognitively to the point that he/she is unable to treat him- or herself, is
240 unable to verbalize his or her needs, is incoherent, disoriented, and/or combative, or experiences seizure
241 or coma. If plasma glucose measurements are not available during such an event, neurological recovery
242 attributable to the restoration of plasma glucose to normal is considered sufficient evidence that the
243 event was induced by a low plasma glucose concentration.
244

245 Definite DKA is defined by the Diabetes Control and Complications Trial (DCCT) as having all of the
246 following:
247

- Symptoms such as polyuria, polydipsia, nausea, or vomiting

- 248 • Serum ketones > 1.5 mmol/L or large/moderate urine ketones
249 • Either arterial blood pH < 7.30 or venous pH < 7.24 or serum bicarbonate < 15
250 • Treatment provided in a healthcare facility

251

252 **8.2 Adverse Events Summary**

253 All episodes of SH, DKA, unanticipated adverse device effects, and any other reportable adverse events
254 will be listed by treatment group. For each event, the following information will be reported:

- 255 • Onset date of the event
256 • Resolution date of the event
257 • Duration of the event
258 • Phase of the trial (run-in phase, pilot period, PLGS phase, or SAP phase)
259 • Description of the event
260 • Intensity of the event
261 • Seriousness of the event
262 • Whether the event was related to the study treatment
263 • Whether the event was related to the study procedure
264 • Whether the event was related to the study device
265 • Whether the event required treatment
266 • Outcome of the event

267

268 Any adverse events that occurred before the randomization visit (i.e., during the run-in or pilot phase)
269 will be tabulated in separate pre-randomization tables in the same manner as the post-randomization
270 adverse events.

271

272 **8.3 Comparison of Safety Outcomes between Treatment Groups**

273 Due to the short duration of the study, it is not anticipated that there will be enough DKA, SH, ketosis (a
274 calendar day with at least one instance of blood ketone level > 1.0 mmol/L), unanticipated adverse
275 device effects, or any other reported adverse events for a formal statistical comparison of the treatment
276 arms. If there are enough events, the following analyses will be performed.

277

278 For each of the following safety outcomes, mean \pm SD or summary statistics appropriate to the

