279 distribution will be tabulated by treatment group:

- 280 • Number of subjects with any DKA events
281 • Number of episodes of DKA events per subject and incidence rate per 100 person years
282 • Number of subjects with any SH events
283 • Number of episodes of SH events per subject and incidence rate per 100 person years
284 • Number of subjects with any ketosis events
285 • Number of episodes of ketosis events per subject and incidence rate per 100 person years

- 286 • Number of subjects with any unanticipated device effects
287 • Number of unanticipated device effects per subject and incidence rate per 100 person years
288 • Number of subjects with any other reported adverse events
289 • Number of other reported adverse effects per subject and incidence rate per 100 person years
290

291 All of the above safety outcomes will be tabulated for all subjects (including dropouts and withdrawals),
292 regardless of whether CGM data are available or whether the device was operational. Any adverse
293 events that occurred before the randomization visit (i.e., during the run-in or pilot phase) will not be
294 included in the rate calculations or treatment group comparisons listed above.
295

296 The number of person-years for the calculation of incidence rates will be defined as the number of
297 person-years from the randomization visit to the last visit date or adverse event date, whichever is later.
298

299 For each of DKA, SH, ketosis, unanticipated adverse device effects, and all other reported adverse
300 events, if there are enough events, rates will be compared using a repeated measures Poisson regression
301 model adjusting for period.
302

303 9. Adherence and Retention Analyses

304

305 9.1 Amount of PLGS and CGM Usage

306 The amount of PLGS and CGM use in hours per week and days per week will be tabulated for each
307 treatment arm (PLGS use will only be for the PLGS arm).
308

309 Summary statistics appropriate to the distribution and range will be reported by treatment group for the
310 days per week and percentage of hours per week of CGM and PLGS use. The percentage of time per
311 week of CGM use will be compared between treatments using the same model described above for the
312 primary outcome.
313

314 Amount of PLGS and CGM usage will further be tabulated by daytime and nighttime (as defined
315 above), but no formal statistical comparison will be made.
316

317 9.2 Protocol Adherence

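### SAP 8.3 extends person-time for the by-treatment safety rates to a late adverse event and does not keep events after pump return out of the PLGS and SAP counts

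*SAP*

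**What the plan says.** SAP section 8 sets the scope of safety reporting: "Safety outcomes will be tabulated by participant for all adverse events from enrollment to the final study" "visit or final adverse event, whichever comes later".

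SAP 8.3 then defines the counts and incidence rates by treatment group. Its denominator is "person-years from the randomization visit to the last visit date or adverse event date, whichever is later". Events before the randomization visit are the only ones not "included in the rate calculations or treatment group comparisons listed above". On the comparison it says: "events, if there are enough events, rates will be compared using a repeated measures Poisson regression". The same section expects too few events for a formal comparison.

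SAP 8.2 gives each listed event one of four labels: "Phase of the trial (run-in phase, pilot period, PLGS phase, or SAP phase".

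Protocol 10.8 uses a different window: "The following safety outcomes will be tabulated by participant within each 3-week treatment period". SAP 5.1 likewise states that every analysis sets the 3-week PLGS period against the 3-week SAP period. At the end of Period 2, under Protocol 5.6.2, "All applicable study supplies will be returned to the clinic".

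**The concern.** The end of follow-up in the rate denominator depends on the outcome. A participant without a late event stops contributing time at the last visit. A participant with one contributes time up to that event. Late events therefore enter the numerator almost without the time at risk that produced them.

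After the Period 2 pump is returned, the participant is on neither trial treatment. SAP 8.3 has no upper cut-off, and the only post-randomization labels in SAP 8.2 are the PLGS and SAP phases. A late event can then be counted against a treatment that had ended. Two analysts following the two documents could report different event counts from the same data.

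**Working it through.** **1. The windows side by side**

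| Place | Events counted | Person-time |
|---|---|---|
| Protocol 10.8 | Within each 3-week treatment period | Not stated |
| SAP 5.1 | 3-week PLGS against 3-week SAP | Not stated |
| SAP 8 | Enrollment to final visit or last adverse event | Not applicable (scope of reporting) |
| SAP 8.3 | Post-randomization, no upper limit | Randomization to last visit or adverse event date, not split by treatment |

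The open end governs the rates through SAP 8.3. The documents state no figure for this point, so there is none to reproduce. SAP 8.3 also does not say whether the adverse event date means onset or resolution.

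**2. Weight of one event**

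Inputs: 90 participants and 21 days per period (SAP section 1).

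- Per treatment: 90 × 21 / 365.25 = 5.17 person-years. One event = 100 / 5.17 = 19.3 per 100 person-years.
- Literal SAP 8.3 span, both periods: 90 × 42 / 365.25 = 10.35 person-years. One event = 100 / 10.35 = 9.7 per 100 person-years.
- The extra time from the event itself hardly matters. For an event 28 days after the final visit, 5.17 + 28/365.25 = 5.25 person-years, and 100 / 5.25 = 19.0.

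**3. How much time the rule adds**

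Assumptions, because the documents give none of these:
- Late events are fully reported for w days after the final visit.
- Each late event is credited to the last-period treatment.
- The rate λ is constant, between 0.2 and 1.0 per person-year.

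With 1:1 order, 45 participants end on each treatment. The added time per treatment is 45 × [w − (1 − e^(−λw))/λ], with λ per day.

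| w | Added by the rule (person-years) | Actually at risk (person-years) |
|---|---|---|
| 7 days | 0.002 to 0.008 | 45 × 7 / 365.25 = 0.86 |
| 14 days | 0.007 to 0.033 | 45 × 14 / 365.25 = 1.72 |

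The rule adds at most about 2% of the time at risk (0.033 / 1.72). The expected number of late events per treatment runs from 0.86 × 0.2 = 0.17 to 1.72 × 1.0 = 1.72.

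**4. Upper bound on the rate**

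Since almost no time is added, a constant rate is inflated by about 1 + w/42:
- w = 7: 1 + 7/42 = 1.17 (1.16 to 1.17 with the added time)
- w = 14: 1 + 14/42 = 1.33 (1.32 to 1.33 with the added time)

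**5. Effect on the ratio**

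Take a true PLGS/SAP rate ratio of 0.50 and a post-return rate equal to the SAP-arm rate (both assumed). The apparent ratio is (10.5 + w/2) / (21 + w/2):
- w = 7: 14 / 24.5 = 0.57
- w = 14: 17.5 / 28 = 0.63

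Here the SAP-arm rate rises by the factors in step 4. The PLGS rate rises more (14 / 10.5 = 1.33 and 17.5 / 10.5 = 1.67, before the small added time), because off-study events are added to a smaller count. That is why the ratio moves toward 1.

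**The case against.** The case against making much of this is substantial.

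- **Scope.** The section 8 sentence starts at enrollment, so it covers run-in and pilot events that 8.3 bars from the comparison. It sets reporting scope and can coexist with Protocol 10.8. This stands. The defect lies in the 8.3 person-time and exclusion rules.
- **SAP 5.1.** It can be read as already confining the comparison to the 3-week periods. This stands in part. The more specific 8.3 says otherwise for person-time, and the two are not reconciled.
- **Attribution.** The SAP never says which treatment a late event is credited to, and SAP 8.2 lists the onset date, so a careful reader would see a late event. This stands. That post-return events are not excluded is in the text; that they will be counted against a treatment is an inference.
- **Ascertainment.** Protocol 5.5 solicits events at contacts and visits. Protocol 8.2.6 provides re-contact only for participants with an adverse event present at completion or who were withdrawn for one. Complete late reporting is therefore unrealistic, and the percentages above are upper bounds.
- **Few events.** The SAP applies the rates and the Poisson model only if events are sufficient. This stands and limits the consequence. The SAP 8.2 listing by treatment group is not conditional in this way.

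**Conclusion.** The point holds as an inconsistency in the safety rates, with a small expected effect. SAP 8.3 makes follow-up depend on having an event and sets no cut-off at pump return, in conflict with Protocol 10.8 and SAP 5.1. One misassigned event is worth about 19 per 100 person-years on a 21-day-per-treatment denominator and about 10 on the 42-day one. Inflation of about 16% (7 days) to 33% (14 days) rests on a constant rate, complete late reporting and last-period attribution. Efficacy is untouched.

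Three stronger readings are not supported:

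- A reader might infer that an Extension Phase event on the PLGS pump would land in the SAP column. The SAP is titled for the randomized crossover trial. Protocol Appendix A gives the extension its own consent and its own tabulation of adverse events.
- A reader might infer that the rule hides harm from PLGS. Order is randomized 1:1, so half the participants finish on each treatment. The result is dilution, not a tilt to one arm, unless late reporting differs by order.
- A reader might infer that Protocol 10.8 discards events after day 21 when a period runs to day 28. The Protocol uses the 3-week label as the name of each study period, and nothing says those days are dropped.

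**What to change.** - **SAP 8.3, events.** For the comparative counts and rates, assign each event by onset date to the pump in use. Each period runs from its start to the pump exchange (Period 1) or return (Period 2), including any days beyond 21. Keep the existing 8.3 rule that events count whether or not the device was operational.
- **SAP 8.3, person-time.** Use the same window, separately for each treatment, and remove the alternative that extends it to an adverse event date.
- **SAP 8.2.** Add a phase for events after the final visit and list them apart from the PLGS and SAP phases.
- **SAP 8.** Keep the sentence, described as the scope of the full listing.
- **Protocol 10.8.** Align it to the same window.

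The cost is a few lines of wording and one phase code. The downside is small: post-return events leave the comparative rates but stay in the listing. The SAP revision history already records data closeout, so the change should be dated and made before the comparative safety tables are produced, or else reported as a later clarification.

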129 Total percentage of time PLGS and CGM is used per week will be calculated by dividing the total number of hours of PLGS readings by the maximum possible number of hours within the study period visit dates described above. Number of days of PLGS and CGM use per week is calculated as the count

132 of days during the week where there was at least one PLGS/CGM reading. Data from both study periods
133 will be included in this analysis. No missing data will be imputed.

134

135 **Hypoglycemic Events**

136 A CGM-measured hypoglycemic event will be defined as:

- 137 • at least 2 sensor values < 54 mg/dl
- 138 • that are 15 or more minutes apart
- 139 • no intervening values > 54 mg/dl
- 140 • Event ends when:
 - 141 ➤ at least 2 sensor values > 70 mg/dl
 - 142 ➤ that are 30 or more minutes apart
 - 143 ➤ no intervening values < 70 mg/dl
- 144 • Participant becomes eligible for a new event as soon as the above criteria for ending the previous
145 event have been met.

146

147 **5. Description of Statistical Methods**

148

149 **5.1 General Approach**

150 All analyses will compare the 3-week period of PLGS to the 3-week period of SAP and will follow the
151 intention-to-treat principle with each period analyzed according to the treatment assigned by
152 randomization regardless of actual PLGS or SAP utilization. All participants who have at least one
153 CGM reading in each 3-week period will be analyzed for the primary and secondary outcomes. All p-
154 values will be two-sided.

155

156 Standard residual diagnostics will be performed for all analyses. If values are highly skewed, then a
157 transformation or nonparametric methods will be used instead. Previous experience suggests that a
158 transformation may be necessary for the hypoglycemic and hyperglycemic outcomes. We do not expect
159 that a transformation will be necessary for some overall glucose control metrics (such as mean glucose).

160

161 **5.2 Analysis Cohorts**

- 162 • All randomized participants who have at least one CGM reading in both 3-week periods will be
163 analyzed for the Intention-to-Treat (ITT) Analysis with each day included in the treatment group
164 assigned by randomization.
- 165 • Safety outcomes will be reported for all enrolled participants, irrespective of whether the study was
166 completed.
- 167 • A per-protocol analysis will be restricted to participants with ≥ 200 hours of CGM data in each 3-

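### SAP 8.3 divides each treatment's adverse events by person-time on both treatments, so each arm's rate per 100 person-years comes out at about half its true value

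*SAP*

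**What the plan says.** Below, SAP means the statistical analysis plan and control means sensor-augmented pump therapy, except inside quotations.

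For each safety outcome, SAP 8.3 says that summary statistics appropriate to the "distribution will be tabulated by treatment group". The list pairs episode counts with rates, for example "Number of episodes of DKA events per subject and incidence rate per 100 person years". The same pairing is used for severe hypoglycemia, ketosis, unanticipated device effects and other reported adverse events. These outputs are conditional: "If there are enough events, the following analyses will be performed".

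Person-years are defined once, for all of these rates, as the "person-years from the randomization visit to the last visit date or adverse event date, whichever is later". The sentence does not mention period or treatment. Events before randomization are excluded from the rates. Where events are numerous enough, rates are also to be compared with a repeated-measures Poisson model that includes period; no exposure offset is named.

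SAP 1 describes two 21-day periods, one treatment in each, every participant receiving both, with no washout. In the event listings of SAP 8.2, each event carries a field for "Phase of the trial (run-in phase, pilot period, PLGS phase, or SAP phase").

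**The concern.** In a parallel-group trial, follow-up from randomization to last visit is the right denominator for each arm. In this crossover the same span covers time on PLGS plus time on control. A numerator restricted to one treatment is then divided by exposure to both.

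The absolute rates are at stake. Protocol 1.1 says the data are intended to support a premarket approval application. Protocol 1.4.1 names hyperglycemia from prolonged suspension as the main device risk and says ketonemia may occur. Ketosis is one of the affected rates. A rate per 100 person-years is a figure readers set beside rates from other settings, and here both treatments, the investigational device included, would look about twice as safe as the data show.

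**Working it through.** The documents state no person-years total or incidence rate, so there is no planned figure to reproduce. The check is person-time arithmetic.

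**Inputs.** At least 90 participants and 21 days per period (SAP 1 and 3); order randomized 1:1 (SAP 3); period-end visit at 21+7 days (Protocol Table 1), so a period may run to 28 days; approximately 100 randomized so that 90 complete (Protocol 2.1). The distribution of dropouts between sequences is assumed.

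**Formulas.** Person-years (PY) = participants × days / 365.25. Rate per event = 100 / PY. Understatement factor for an arm = PY on that treatment / PY as written. The rate ratio as written, divided by the true rate ratio, equals PY on PLGS / PY on control.

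**Base case: 90 completers, 21 days in each period.**
- PY on each treatment: 90 × 21 / 365.25 = 5.175.
- PY as written: 90 × 42 / 365.25 = 10.349.
- Rate per event: 100 / 5.175 = 19.3 on own-treatment time; 100 / 10.349 = 9.7 as written.
- Factor: 5.175 / 10.349 = 0.50. The number of participants cancels, so this holds at any sample size with equal periods.

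**Sensitivity.** The rate columns show own-treatment time, then as written, per event.

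| Scenario | PY PLGS | PY control | PY as written | PLGS rate | Control rate | Factor PLGS / control | Rate-ratio distortion |
|---|---|---|---|---|---|---|---|
| 90 completers, 21/21 d | 5.175 | 5.175 | 10.349 | 19.3, 9.7 | 19.3, 9.7 | 0.50 / 0.50 | 1.00 |
| 90 completers, 28/28 d | 6.899 | 6.899 | 13.799 | 14.5, 7.2 | 14.5, 7.2 | 0.50 / 0.50 | 1.00 |
| Period 1 21 d, Period 2 28 d, sequences 45/45 | 6.037 | 6.037 | 12.074 | 16.6, 8.3 | 16.6, 8.3 | 0.50 / 0.50 | 1.00 |
| Every PLGS period 21 d, every control period 28 d | 5.175 | 6.899 | 12.074 | 19.3, 8.3 | 14.5, 8.3 | 0.43 / 0.57 | 0.75 |
| 100 randomized, 10 leave after Period 1, 5 per sequence, 21 d | 5.462 | 5.462 | 10.924 | 18.3, 9.2 | 18.3, 9.2 | 0.50 / 0.50 | 1.00 |
| As above, all 10 from PLGS-first | 5.749 | 5.175 | 10.924 | 17.4, 9.2 | 19.3, 9.2 | 0.53 / 0.47 | 1.11 |

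The fourth and last rows are deliberate extremes. Randomized order makes it unlikely that every long period falls on one treatment, or that every dropout falls in one sequence. Dropout matters at all because "All of the above safety outcomes will be tabulated for all subjects (including dropouts and withdrawals").

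Protocol 5.5 prints the period-end window as 21 ± 7 days where Table 1 prints 21+7. If 14-day periods were possible, an equally contrived case of 14 days on one treatment and 28 on the other gives factors of 14/42 = 0.33 and 28/42 = 0.67, with the rate ratio off by a factor of two. This widens the extremes and leaves the central value at 0.50.

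The adverse-event-date extension adds little: assuming 14 extra days in 5% of participants, 21 / (42 + 0.05 × 14) = 0.49.

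**The case against.** The strongest reply is that no competent statistician would compute it this way. SAP 5.1 says "All analyses will compare the 3-week period of PLGS to the 3-week period of SAP", SAP 8.2 assigns events to phases, Protocol 10.8 tabulates safety within each 3-week treatment period, and a Poisson model with a period term implies one record per participant per period. SAP 5.2 allots each day to the treatment assigned by randomization. On this reading, the person-years sentence only sets the outer limits of follow-up, and the split by treatment applies within them.

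That shows what was probably intended, but not what is specified. None of those passages defines person-time for the safety rates. The SAP 5.2 phrase belongs to the intention-to-treat bullet for CGM analyses, not to the safety bullet. The only sentence that defines the denominator gives a different one, so a programmer who follows it gets the wrong rate and one who follows the intent departs from the SAP. The table shells are a separate document and were not available; even if they split the time, the SAP would still state otherwise.

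The reply is right that the harm is limited. SAP 8.3 does not anticipate enough events for formal comparison, so the rates may never be produced. Protocol 10.8 asks for no person-year rates. Counts and numbers of subjects with events sit alongside the rates, so an alert reader could notice a factor of two.

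**Conclusion.** The concern holds. As written, the denominator in SAP 8.3 understates each arm's absolute incidence rate by a factor of about two: 9.7 instead of 19.3 per 100 person-years per event, with 90 completers and 21-day periods. The factor is 0.50 whenever total time on the two treatments is equal, and close to 0.50 under any plausible mix of visit timing and dropout.

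The comparison between treatments is largely safe. The rate ratio is undistorted with equal time on treatment and moves materially only in the contrived cases above. Counts, subjects with events, episodes per subject and listings do not use person-years. Neither do the pilot safety metrics in Protocol 4.4 or the stopping criteria in Protocol 8.6. The error therefore bears on descriptive absolute rates that are produced only if events are numerous enough. It should be fixed, but it does not threaten the trial's main conclusions.

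**What to change.** Replace the person-years sentence in SAP 8.3 with a definition per participant and per treatment period:

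- Period 1 time runs from randomization to Period 2 initiation, or to withdrawal if earlier.
- Period 2 time runs from Period 2 initiation to the final visit, or to withdrawal if earlier.
- Each treatment's rate uses only the time in the periods assigned to that treatment.
- If the Poisson model is fitted, the logarithm of this time is the offset.
- Any extension to an adverse-event date is added only to the treatment period to which that event is assigned. The SAP should state how an event dated after the final visit is assigned.

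The event window in SAP 8, which ends at the final study "visit or final adverse event, whichever comes later", can stay, as can the exclusion of pre-randomization events from the rates.

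The cost is minor wording and programming. SAP 4.3 already relies on the Period 1 initiation, Period 2 initiation and final visit dates; only those dates are needed, not the 21-day cap it places on CGM data. The events counted do not change, and neither do trial conduct, data collection or the primary analysis. Reported absolute rates become about twice as large.
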